**Phase 3/Aim 3: Test Phase (18 months)**. We will conduct a pilot study comparing the tCBT training that includes the ITS program (from the *Design/Build* phase) to the traditional training program and its impact on time to learning tCBT and competency delivering tCBT. Latino bachelor-level social work and nursing students from Heritage University will be invited in the Spring quarter of their junior year to apply to participate in our specialized program. We will randomize 10-12 students in years 1 and 2 (two successive cohorts of 5-6 students each) during the study and each will work with five patients using tCBT

**Patient eligibility.** Sixty patient participants will be identified through Yakima Valley Farmworker’s Clinic electronic health record. Participants must be 18 years old or older, suffering from mild to moderate depression with PHQ-9 scores of 10-20. Identified patients will be contacted by a Methods Core research assistant to conduct a preliminary screening for eligibility, provide a brief description of the study and obtain informed consent.

**Paraprofessional Data Collection.** After training, paraprofessionals will be assigned a total of 5 cases each to assess paraprofessional capacity to conduct tCBT. Two types of data will be collected—paraprofessional

assessment of tCBT usability, and ability to learn tCBT and maintain competency. To measure **intervention usability**, paraprofessionals will complete the ALFA-Q Acceptability Scale, the User Burden Scale (UBS) and the System Usability Scale (SUS), which are core measures for this center (see **Methods Core** for description of scales). These scales will be collected through the UWAC data portal after initial training in tCBT after they have seen their 5th patient. **Learnability** of the tCBT will be measured as time to reach competency during training. To measure **sustained competency**, paraprofessionals will collect audio recordings of patient sessions for review by experts. Drs. [name] and [name] will conduct these reviews using the Cognitive Therapy Scales (CTS) adapted to apply to structured, manualized telephone CBT. The CTS utilizes a 7-point rating scale (0 = *poor*, 6 = *excellent*) and has been used to assess the competence of paraprofessional therapists. Sustained competency will be defined by (1) time to first session rated below average and (2) number of sessions rated below average.

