**Data Analysis.** Aim 3 focuses on pilot feasibility data to inform a larger (future) clinical trial comparing ITS-based training in tCBT to training-as-usual (TAU). Thus, analyses do not focus on hypothesis-driven inferential statistics but on descriptive statistics, graphical summaries, and basic effect sizes. H1: Usability. Differences in clinician-reported usability between ITS training and TAU will be plotted using a dotplot and tested using a *t*-test using the ALFA-Q, SUS, and UBS as dependent variables. H2: Fidelity/Competence: A similar strategy (dotplot, *t*-test) will be used with number of hours to reach certification. Number of sessions with CTS scores in competent range will be summarized as proportions, both by clinician and by treatment. Between-group differences will be tested with a 2-sample proportion test. (Future analyses with larger sample size will use a generalized linear mixed model approach to account for the nested data.) H3: Patient-Reported Outcomes. Histograms and kernel density estimates will be plotted by treatment condition to explore differences on depression outcomes (PHQ-9 total score) and overall daily functioning (SDS). Descriptive statistics (*M* and *SD*) will also be examined by clinician and by treatment, using Cohen's *d* as an effect size summary. A *t*-test will be used to examine treatment differences in patient outcomes. Of ultimate interest is whether the modified training protocol (i.e., ITS vs. TAU) has its impact on patient outcomes through enhanced learnability via clinician competence/fidelity. We will use graphical summaries of the data to explore the relationships that are consistent with mediation (e.g., correlation of usability with patient outcomes [b pathway], and treatment differences on patient outcomes with fidelity partialled out [c' pathway']). The primary focus here is whether the data and relationships appear consistent with mediation, as opposed to a formal test, which will be dramatically under-powered.

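### The c' mediation summary partials out fidelity rated on the outcome patients' own sessions, with no patient covariate and no stated unit of analysis, so case difficulty can distort it

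*Combined protocol and SAP*

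**What the plan says.** All of this is in the APPROACH section.

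- **Source of the fidelity rating** (Paraprofessional Data Collection): "paraprofessionals will collect audio recordings of patient sessions for review by experts", scored on the CTS. No competence rating from outside trial sessions, such as a standardised role-play score, is named as the mediator.
- **Definition of competence** (same paragraph): "Sustained competency will be defined by (1) time to first session rated below average and (2) number of sessions rated below average". Data Analysis adds that sessions in the competent range will be "summarized as proportions, both by clinician and by treatment".
- **Outcomes** (Patient data collection): PHQ-9 and SDS from the treated patients, before and after treatment. A baseline value of each is therefore available.
- **Mediation** (Data Analysis): the c' summary is "treatment differences on patient outcomes with fidelity partialled out". The correlation given as an example of the b pathway is between usability and patient outcome. "The primary focus here is whether the data and relationships appear consistent with mediation", and the plan says that a formal test would lack power by a wide margin.
- **Size** (Phase 3/Aim 3): "We will randomize 10-12 students in years 1 and 2", and "paraprofessionals will be assigned a total of 5 cases each to assess paraprofessional capacity to conduct tCBT".

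**The concern.** Randomising students protects the comparison of arms. It does not protect the relation between the mediator and the outcome, because nobody randomises how well a given session goes. A severely depressed or poorly engaged patient can make a session harder to deliver well and can also end with a worse score. That common cause produces a fidelity-outcome association without any effect of competence.

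The plan says that this mechanism is what it ultimately wants to learn about, and the judgement is to be made by looking at plots and partialled differences. Conceding low power deals with imprecision. It does not deal with a bias that runs in one direction, towards the mechanism the investigators expect. The unit of analysis also matters, because the size of the distortion depends on whether CTS enters by patient or by student, and the plan does not say which.

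**Working it through.** **1. The plan's own figure.** "Sixty patient participants will be identified through Yakima Valley". With 12 students and 5 cases each, 12 × 5 = 60, which agrees. With 10 or 11 students the product is 50 or 55. The calculations below use 12 × 5. The plan states no mediation effect, correlation or power to reproduce.

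**2. Set-up (assumptions, not in the documents).** Let S be patient difficulty, X the CTS rating of a patient's sessions (higher is better) and Y the final score (higher is worse), each with SD 1. Let corr(S, X) = p, corr(S, Y) = q, and the true effect of X on Y be zero. The between-student ICC of CTS is 0.3. CTS is treated as continuous, whereas the plan counts sessions against a threshold.

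**3. Spurious correlation.**

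- Same-patient pairing: r = p·q.
- Student-mean CTS against each patient's outcome: the student mean has variance 0.3 + 0.7/5 = 0.44 (SD 0.663), and one fifth of it is the patient's own rating. So r = (p·q/5)/0.663.
- Student means on both sides: the mean outcome has variance 1/5 (SD 0.447), so r = (p·q/5)/(0.663 × 0.447) = (p·q/5)/0.297.

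| p, q | Same patient | Student-mean CTS, patient outcome | Student means on both sides |
|---|---|---|---|
| -0.2, 0.4 | -0.08 | -0.016/0.663 = -0.02 | -0.016/0.297 = -0.05 |
| -0.3, 0.5 | -0.15 | -0.030/0.663 = -0.05 | -0.030/0.297 = -0.10 |
| -0.4, 0.6 | -0.24 | -0.048/0.663 = -0.07 | -0.048/0.297 = -0.16 |

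Simulation of 12 × 5 trials agrees. Averaging by student dilutes the artefact but does not remove it, because the student's score still contains the same five patients.

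**4. Effect on c'.** Suppose training raises CTS by a = 0.5 SD and changes the outcome by c = -0.40 SD, none of it through competence. Then c' = c - a·b, where b is the spurious within-arm slope.

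- Same patient: b = p·q. So c' = -0.40 + 0.5 × 0.08 = -0.36, then -0.40 + 0.5 × 0.15 = -0.325, then -0.40 + 0.5 × 0.24 = -0.28. Simulation at this sample size gives about -0.27 for the last.
- Student mean: b = (p·q/5)/0.44, which is -0.036, -0.068 and -0.109. So c' = -0.38, -0.37 and -0.35.
- If a = 0, then c' = c on average whatever p and q are.

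**5. Sensitivity to the model.** A separate simulation made the outcome depend more strongly on difficulty (coefficient 0.71), with a pull of difficulty on the rating of 0.3 or 0.5. For the same true -0.40 it gave c' of -0.26 or -0.18 with same-patient pairing, and -0.34 or -0.30 by student. With no pull on the rating, c' stayed at -0.40.

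**6. How well the remedies work.**

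- *Baseline adjustment.* If baseline captured difficulty perfectly, the spurious correlation would go to 0. Suppose instead that baseline correlates 0.5 with true difficulty (an assumption), with p = -0.3 and q = 0.5. Baseline then correlates -0.15 with X and 0.25 with Y. The partial correlation is (-0.15 + 0.15 × 0.25)/√[(1 - 0.0225)(1 - 0.0625)] = -0.1125/0.957 = -0.12. At 0.3 instead of 0.5 it is -0.14.
- *CTS from the student's other patients.* The patient's own difficulty no longer enters the score, and the simulated correlation is about 0 (about 0.01 at p = -0.3, q = 0.5). In the setting of step 4, c' is about -0.41 to -0.42, a small bias the other way.

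**The case against.** The case against making much of this has four parts.

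- **Pairing.** A reader might infer that each patient's outcome will be set against the ratings of that same patient's sessions. The documents do not say so. They define competence by student and summarise it by clinician and by treatment. This stands, so the student-level figures are the closer reading and the same-patient figures are an upper case under the same assumptions.
- **The named correlation.** The b-pathway example uses usability, which is the student's self-report and is not rated from patient sessions. This stands for that correlation. It does not reach the c' summary, which names fidelity.
- **Whether difficult patients are enough.** A reader might infer that hard cases alone would make the data look like mediation. They would not do so on average. With no arm difference in rated competence, c' equals c. A systematic false pattern also needs training to raise CTS, which is what H2 predicts.
- **Proportion.** With 12 student points, a correlation of -0.15 or stronger occurs in 32% of simulated trials with no confounding and in 45% with it (p = -0.3, q = 0.5), so noise accounts for most of that risk. The plan presents the check as graphical and exploratory. This stands and limits the importance of the point.

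The Specific Aims also word the PHQ-9 outcome as change over time, which would bring baseline in for that scale. Data Analysis names only the total score, and neither place says this for the SDS.

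**Conclusion.** The point holds in a limited form. Fidelity is rated on sessions of the patients who supply the outcomes, the c' summary names no patient covariate, and the unit is unstated. The fidelity-outcome relation is therefore open to confounding by case difficulty, which randomising students does not remove. Where training raises CTS, c' can fall short of c without any mediation.

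Under the main assumptions the distortion is small to moderate. By student, a true -0.40 SD reads as -0.38 to -0.35, and with same-patient pairing as -0.36 to -0.27. These figures rest on assumed correlations, an assumed ICC of 0.3 and continuous CTS. If ratings do not fall with difficult patients, there is no distortion. The documents do not support a claim that the mediation reading will be wrong, or that it would settle the design of the later trial. This is a modest improvement to consider.

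**What to change.** In the mediation part of Data Analysis:

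1. State the unit of analysis for each mediation summary (patient or student) and which CTS summary enters it.
2. Adjust the fidelity-outcome and c' summaries for the patient's baseline PHQ-9 or SDS, matching the outcome. State that this removes only the part of patient difficulty that baseline captures.
3. Show a companion version that sets each patient's outcome against the mean CTS of that student's other patients. State that this score is noisier (four cases instead of five) and has a small opposite bias in c'.
4. Plot one point per student, so that the reader sees how few independent competence values there are. Note that student means on both sides still carry the diluted artefact.
5. Add a sentence that agreement with mediation may partly reflect case difficulty.

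The cost is a few sentences and a few lines of code. No new data are needed.

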Remote Training in Evidence-based Practices for Clinicians who Work with Migrant Workers

NCT03515226

July 30, 2020

**SPECIFIC AIMS.** Per the Institute of Medicine (IOM) report on Psychosocial Standards, the US suffers from a dearth of clinicians who can offer evidence-based psychosocial interventions (EBPI). This limited **clinical capacity** is due to poor preparation of clinicians before they enter the workforce and variable quality of graduate and postgraduate training. The main challenge in training clinicians in EBPIs is the complexity of the interventions (Study 2), and the numerous decisional dilemmas clinicians face when using EBPIs in care (Study 3). To effectively train clinicians in EBPIs, trainees must undergo in-depth education, intensive skill building and close supervision. As an example, the Increasing Access to Psychological Treatment (IAPT) clinician training program requires 6 months to one year of postgraduate training, which includes 1-2 days a week in didactics, scaffolding skill building, and close, videotape-guided supervision. Thus, a major barrier to building capacity is the lack of time-efficient and educationally effective EBPI training models. Innovations in computer science and adaptive training algorithms may provide a way to train clinicians in effective use of EBPIs. Early evidence on these programs finds that they effectively reduce time in training, improve competence in complex decision-making and standardize training. As an example, a recent study funded by the Defense Advanced Research Projects Agency (DARPA) found that an intelligent tutoring system (ITS) for naval engineers not only reduced training time by 18 months, but graduates of this program were more competent than engineers who were trained traditionally and had been in the field 10 years. Our proposed study builds on the existing research base on EBPI training, and adds to it by designing and testing a computerized training program (ITS) based on adaptive training algorithms. We hypothesize that capacity building through improved EBPI learnability (target mechanism) will result in enhanced clinical ability to deliver EBPI elements competently, in a shorter time period, and that greater competence will result in better quality of care (Fig. 2). The data from the current R34 will serve to inform a R01 proposal to test the comparative scalability, implementation costs and training effectiveness of computerized training versus training-as-usual.

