
**Aim 1. Discover Phase (3 months)** Using iterative and participatory methods, we will work with 10 paraprofessionals who had been trained in telephone-based cognitive behavioral therapy (tCBT) to discover challenges they face in delivery of tCBT, identify areas in the traditional curriculum that supported their skill acquisition, and areas that were missing from the training. Feedback from study team members with expertise in teaching bachelor-level students and other key stakeholders will help inform this process. This information will be used to build the adaptive algorithm in Aim 2. Contribution to the Center: Because the process of educational development includes the identification of competencies that are challenging to learn, data from this phase will be used to inform the Typology of EBPI Targets.

**Aim 2. Design and Build Phase (9 months).** After identifying educational modification targets, and key decisional dilemmas to be built into the program, we will build an Intelligent Tutoring System (ITS) in tCBT via rapid iterative design. The 6 trainees who participated in the *Discover* phase will be actively involved in the *Design/Build* phase, in conjunction with educational experts in tCBT. Contribution to the Center: Data from this phase will be used to inform the Matrix of EBPI Modifications.

[figure not shown]
**Aim 3: Test Phase (18 months).** We will test and compare the addition of an ITS in tCBT to training-as-usual in a small-scale randomized controlled trial. Ten to twelve students will be randomized to the two conditions.

**H1:** The ITS will result in better rating of tCBT usability (AFLA-Q Acceptability, System Usability and User Burden Scales), and student confidence in using tCBT compared to traditional training. **H2:** Students

randomized to the ITS will certify faster (hours in training), and will more competently deliver tCBT elements (number of sessions rated below standard by experts and time to first session rated below standard) than clinicians randomized to traditional training. **H3:** Patients treated by computer-trained students will report better outcomes on functional disability (SDS; Sheehan Disability Scale), and change in depression symptoms over time (PHQ-9 total score) than those treated with traditionally trained students. We will conduct preliminary analysis to determine if change in clinical outcomes is mediated by clinician quality.

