**Training program in telephone-based CBT (tCBT).** tCBT consists of 8 sessions delivered over 10 to 12 weeks. Each session is designed for delivery in 35 - 40 minutes and includes: structured assessment of depressive symptoms (5 min); review of prior session content (5 min); debriefing previous homework assignment (5-10 min); introduction of new material, including in-session examples and exercises (15-20 min); description of the new homework assignment (5-10 min); and a motivational assessment/enhancement exercise focused on the homework assignment (5 min). The current tCBT training program has four key elements: 1) training program content, designed to target competencies of knowledge and attitude, competence in delivering CBT, and fidelity to the treatment; 2) teaching methods, targeting both the cognitive domain (principles and guidelines needed to deliver EBPI) and the affective domain (attitudes and values related to EBPI); 3) simulated case training to practice skills; and (4) teachers and supervisors to provide on-going skill building with actual patients.

Figure 1. DBBT Model for Research Study.

**Study Overview.** To accomplish the aims of the study, this project will be broken down into 3 phases that are tied to each aim of the study: *the Discover phase*, (Aim 1), *the Design and Build phase* (Aim 2), and *the Test phase* (Aim 3; see Fig. 1. For phases 1 and 2, we will work with 10 paraprofessionals who have been trained in tCBT using the traditional mode described above. For phase 3, we will recruit 2 successive cohorts of 5-6 bachelor students from Heritage University and randomize them to the traditional training model and the new adaptive learning method. The study will be conducted over a 2.5 year period during Y01 through Y03. Steps 1 and 2 will be conducted in the first 9 months of the study and Step 3 in the last 15 months (See timeline).

**Phase 1/Aim 1: Discovery (3 months).** The purpose of this phase is to identify key competencies and decisional dilemmas trainees experience when learning tCBT. Drs. [name] and [name] will be responsible for data collection and synthesis in this phase. As is detailed in the **Methods Core**, *Discover* phase data collection involves the identification of user needs, contextual evaluation, and user testing.

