**Power and Sample Size.** Sample sizes for Aims 1 and 2 were based on estimates from the user-centered design literature on necessary number of participants to capture critical design information, where the recommendation is 5-10 end users. Aim 3 is focused on gathering information (feasibility, recruitment and retention rates, response and attrition rates, etc.) for a future R01 application. Thus, the sample size was set primarily for practical reasons and driven by estimated effect sizes rather than hypothesis testing..

**Timeline.** This study will begin in Y02 of the Center. The *Discover* phase activities will be completed in 3 months. The *Design/Build* phase will be completed in 9 months. The *Test* phase will take 18 months, of which identification and training of clinicians in the two interventions will take approximately 2 months for each cohort. Patient recruitment and data collection will take 10 months. Data analysis will take 3 months.

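### The pilot's effect sizes are planned without confidence intervals, although the expected 95% half-width is about 1.3 to 1.5 SD for student outcomes and 0.6 to 0.9 SD for patient outcomes

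*Combined protocol and SAP*

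**What the plan says.** All references are to the combined protocol and SAP.

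- **Purpose.** SPECIFIC AIMS states: "The data from the current R34 will serve to inform a R01 proposal to test the comparative scalability", among other properties of computerised training. Data Analysis likewise presents Aim 3 as a feasibility pilot for a later, larger trial.
- **Size.** SPECIFIC AIMS, Aim 3: "Ten to twelve students will be randomized to the two conditions". The Test Phase section describes two successive cohorts of five or six students. The Study Overview says the team will "randomize them to the traditional training model and the new adaptive learning method", without an allocation ratio.
- **Patients.** In the Test Phase section, "Sixty patient participants will be identified through" the clinic's health record, and "paraprofessionals will be assigned a total of 5 cases each".
- **Basis of the size.** Power and Sample Size: "the sample size was set primarily for practical reasons and driven by estimated effect sizes rather than hypothesis testing". No effect size, SD, ICC or target precision accompanies this.
- **Analysis.** Data Analysis puts description, plots and simple effect sizes ahead of inference. Usability scores (H1) and hours to certification (H2) get a dotplot and a t-test. Session competence (H2) gets a two-sample proportion test. For PHQ-9 and SDS (H3), means and SDs are given by clinician and by arm, with Cohen's d "as an effect size summary" and a t-test. Models for nested data are left to later, larger studies. No confidence interval is mentioned for any outcome.

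**The concern.** If a pilot exists to estimate rather than to test, its estimates need a statement of how well they are determined. As planned, a reader of the results would have a point estimate and a p-value for each outcome, but no range of effects compatible with the data. With this few randomised students, that range runs from a difference in the wrong direction to a very large benefit. A bare d of, say, 0.5 would look far more settled than it is.

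H3 carries a second risk. Patients are nested within the students who were randomised. An interval added as an afterthought, treating the patients as independent, would be too narrow.

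**Working it through.** **Inputs from the document.** 10 to 12 randomised students; 5 patients per student; 60 patients stated.

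**Consistency of the stated figures.** 2 cohorts × 5 or 6 = 10 or 12 students. 12 × 5 = 60 patients, which matches the stated 60; with 10 students the total is 10 × 5 = 50. The basis of the student number cannot be reproduced, because no effect size, SD or precision is given.

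**Assumptions, none of them stated in the document.** 1:1 allocation (5 v 5 or 6 v 6), no dropout, equal clusters of 5, two-sided 95% intervals, and an ICC of patients within student between 0 and 0.2.

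**1. Student-level outcomes (usability scales, hours to certification).** Half-width in SD units = t(0.975, 2n − 2) × √(2/n), with n students per arm.

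- n = 5: 2.306 × √(2/5) = 2.306 × 0.632 = 1.46 SD
- n = 6: 2.228 × √(2/6) = 2.228 × 0.577 = 1.29 SD

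Unequal splits give similar values: 1.49 for 4 v 6 and 1.37 for 5 v 6. The exact noncentral-t interval for an observed d of 0.5 is −0.78 to 1.75 (5 v 5) or −0.66 to 1.64 (6 v 6). These are somewhat narrower, with half-widths of about 1.27 and 1.15, but still above 1 SD.

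**2. Patient-level d (PHQ-9, SDS).** With k students per arm, the design effect is DE = 1 + (5 − 1) × ICC, and the half-width is t(0.975, 2k − 2) × √(2 × DE / 5k). The degrees of freedom are students minus 2.

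| ICC (assumed) | DE | 60 patients, t on 10 df | 50 patients, t on 8 df |
|---|---|---|---|
| 0 | 1.0 | 0.58 | 0.65 |
| 0.05 | 1.2 | 0.63 | 0.71 |
| 0.10 | 1.4 | 0.68 | 0.77 |
| 0.20 | 1.8 | 0.77 | 0.88 |

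For example, 60 patients at ICC 0.20: 2.228 × √(2 × 1.8/30) = 2.228 × 0.346 = 0.77.

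Treating patients as independent gives 0.52 (60 patients) or 0.57 (50 patients). At ICC 0.20 that is about two-thirds of the proper width: 0.52/0.77 = 0.68 and 0.57/0.88 = 0.65. The half-width would pass 1 SD only with an ICC above about 0.51 (60 patients) or 0.34 (50 patients).

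**3. Small-sample bias in d.** The correction factor is J = 1 − 3/(4df − 1).

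- Student level: 1 − 3/31 = 0.903 (8 df) and 1 − 3/39 = 0.923 (10 df). Uncorrected d is inflated by about 8 to 11%.
- Patient level: 1 − 3/191 = 0.984 (48 df) and 1 − 3/231 = 0.987 (58 df). The inflation is about 1.3 to 1.6%, which is negligible.

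**The case against.** The strongest reply is that imprecision is inherent in a pilot of this size and that the plan is open about its limits. It sets inference aside as a focus, leaves nested modelling to larger samples, and says a formal mediation test would have far too little power. A dotplot of 10 to 12 students also shows the spread directly. This stands as a reason to treat the point as minor. It does not remove the point: the candour about mediation is not extended to the effect sizes, and a dotplot is not an interval for a difference.

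Three stronger readings are tempting, and the document does not support them.

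- **That the R01 will be sized on the pilot's d.** A reader might infer this from the emphasis on effect sizes and on a later trial. The document never says so. What Power and Sample Size lists for the R01 is feasibility, recruitment, retention, response and attrition.
- **That the planned Cohen's d is uncertain by more than 1 SD either way and inflated by about a tenth.** Those are student-level figures. Cohen's d is named only for H3, where the half-width is about 0.6 to 0.9 SD under the assumed ICCs and the bias is about 1.5%.
- **That the sample-size sentence is false.** It puts practical reasons first, and its second half can be read as aiming at estimation rather than testing. On that reading no prior effect size was ever claimed. The wording is ambiguous, not shown to be wrong. If estimation is the aim, though, the expected precision is the natural thing to state.

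**Conclusion.** The point holds as a minor reporting gap. Effect sizes are a main output of a pilot meant to inform a larger trial, and no interval is planned for any of them.

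The expected 95% half-width is about 1.3 to 1.5 SD for student-level differences. It is about 0.6 to 0.9 SD for the patient-level d in H3. Both rest on 1:1 allocation and no dropout. The H3 range also rests on equal clusters of five, t on students minus 2 df, and an ICC of 0 to 0.2, which is an assumption. On this range, an observed d of 0.5 would be compatible with no effect and with a very large one, at either level.

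Nothing here faults the choice of 10 to 12 students for practical reasons, or alleges a misuse of d in the later application.

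**What to change.** **Data Analysis.**

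- Report every H1 to H3 between-arm difference with a 95% confidence interval.
- For student-level standardised differences, use Hedges' g.
- For H3, use an interval that respects the student as the randomised unit. Either an analysis of student means or a design-effect-adjusted standard error with t on students minus 2 df would do. State the ICC that is used or estimated.
- Apply the same principle to the H2 session proportions, since sessions are also nested within students.

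**Power and Sample Size.** Say that the size was set for practical reasons. In place of the reference to estimated effect sizes, give the expected precision: about ±1.3 to 1.5 SD for student outcomes and about ±0.6 to 0.9 SD for patient outcomes, with the assumptions above.

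**Cost.** A few sentences and a small amount of extra analysis; no more participants or data. The intervals will be wide, and the stated precision will look less favourable than bare point estimates.
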